The AVERT study addresses an enormous obstetrical problem having a large unmet need with the use of a novel risk assessment tool (PreTRM®) and established multimodal interventions administered within the single ChristianaCare hospital network. However, there are several potential limitations to the AVERT study. Comparisons to historical controls can be susceptible to selection bias and epoch effects. Subjects who don't accept interventions may add self-selection bias. As well, AVERT is subject to a research halt due to the spread of SARS-CoV-2, avoiding a pandemic epoch effect while restricting study size.

This statistical analysis plan addresses the study objective of evaluation of the PTB prevention strategy while overcoming potential study limitations. The original endpoints are replaced with more powerful endpoints aligned to the study size and faithful to the study's goal of reducing adverse outcomes. The primary analysis is in a modified ITT population enabling comparison of the fully consented PTB prevention strategy population to a population who received standard care. To adjust for any bias in consent to intervention, exploratory analyses compare subjects accepting and not accepting interventions, and address the efficacy of individual intervention components.

An estimated 1,453 prospective subjects reached a gestational age of $37^{0/7}$ weeks before local spread of SARS-CoV-2 in Delaware and the associated shut-down of non-COVID-19 research at ChristianaCare. Approximately 10,000 historical controls were selected

from a period of about 2 years immediately prior to study initiation. The study design shows at least 86% power for 5% alpha shared across two co-primary endpoints: neonatal morbidity and mortality index and neonatal length of total hospital stay.

The funder, Sera Prognostics, will remain blinded to all clinical data until a formal communication of topline results from this analysis is made.

Background: Preterm birth (PTB) remains the leading cause of neonatal mortality and long term disability throughout the world. Recently treatments early in pregnancy such as progesterone, cervical support and maternal support have been demonstrated to delay delivery amongst at risk women. Nonetheless, the majority of women who are at risk are not identified using current screening modalities.

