Hypothesis: A cohort of pregnancies who are screened using the PreTRM® test around 20 weeks gestation in which a bundle of interventions is given for elevated PreTRM® risk will show either decreased neonatal morbidity/and mortality (measured as a composite score, “NMI”), or decreased length of neonatal stay in the hospital (NNOLOS). Secondarily, they will show an increase in gestational age at birth (GAB) and a reduction in length of neonatal NICU stay (NICULOS), compared to an unscreened historical control group.

Study Design Type: Prospective cohort study of screened pregnant women compared to a historical control.

Population: Prospective subjects are recruited from ChristianaCare’s patient population as described in the study protocol. A comparable control population will be identified from ChristianaCare’s database, as described in the study protocol. A total of approximately 10,000 women meeting the screening protocol will be identified with delivery prior to July 6th, 2018. Women will be sequentially identified retrospectively who qualify for the study based on applicable inclusion and exclusion criteria. As such cohort definition dates can only be estimated but are noted with a delivery of volume of approximately 6,000 deliveries a year, this would approximate a start date for the historical cohort of August 6th, 2016.

Intervention: Qualifying women will be screened using the PreTRM® test (Sera Prognostics, Inc.) at a large tertiary care center. Predicated upon the degree of risk based on a prespecified algorithm that includes height, weight, and measurement of two serum proteins (IBP4 and SHBG), women will be treated according to a pre-determined protocol. The outcomes of the screened cohort of women will be compared to those of the historical control group at the same tertiary care center.

Outcomes:

Co-Primary outcomes: To determine whether a cohort of women who are screened with the PreTRM® test and then managed according to a prespecified protocol will have statistically significant reductions in either (a) composite neonatal morbidity and mortality (NMI score), or (b) length of neonatal hospital stay (NNOLOS), compared to a historical control group.

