- Length of neonatal NICU stay (NICULOS): days from admission to neonatal intensive care (NICU) to neonatal discharge home from the NICU or until death if occurring before discharge. This includes all levels of care designated by ChristianaCare as intensive care, including all transfers across levels of intensive care. Nursery and non-intensive care days are not included. This will be calculated in fractional days if times of admission and discharge are available and rounded to the nearest integer value of total days, or as the number of total days in intensive care if times are not available; times are not required. NICULOS is set to zero for babies never admitted to the NICU but admitted to the hospital. In cases of stillbirth or neonatal mortality in the NICU, NICULOS is set to one day longer than the maximum length of stay recorded for any infant. NICULOS will be truncated at $44^{0/7}$ weeks of gestational age as specified in the protocol.

- Duration of gestation: GAB is set to $40^{0/7}$ weeks for deliveries on the estimated due date (EDD) and adjusted by the difference in days between the date of delivery and the EDD for all other births. The EDD is established by ultrasound data or accurately known last menstrual period (LMP), according to ACOG guidelines, as described in the protocol.

Safety outcomes: monitoring of adverse events is described in the protocol.

4. Determination of Sample Size

This study has been terminated due to the advent of the SARS-CoV-2 pandemic in the ChristianaCare population. At study termination, 1,873 subjects were enrolled in the study. To avoid bias in comparison of pre-pandemic controls to prospective subjects who reached term during the pandemic period, the primary analysis of the study will be limited to an estimated 1,453 subjects who reached $37^{0/7}$ weeks gestation before local spread of SARS-CoV-2 in Delaware and the associated shut-down of non-COVID-19 research at ChristianaCare.. Approximately 10,000 historical controls were selected from a period of about 2 years immediately prior to study initiation.

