5.7 Exploratory Analyses

In AVERT, there is a challenge and opportunity in the moderate rate of acceptance of intervention among high-scoring women in the intervention arm. The exploratory analyses include options for addressing the non-accepting completers in the prospective arm, and comparing them to those in mITT and the compliant completers.

The exploratory outcomes will be summarized within the prospective arm and within historical controls using descriptive statistics and graphical displays where appropriate. Continuous outcomes will be summarized using sample size (n), means, medians, standard deviations, and ranges. Categorical outcomes will be summarized using frequency and percentages. Estimates will be presented with 95% confidence intervals. Exploratory summaries will be performed for the mITT population.

The following exploratory endpoints will be evaluated by a test of proportions in the prospective arm versus historical controls. The null hypothesis is no difference between historical controls and the prospective arm. The alternative hypothesis is relative reduction in proportion of occurrence of one or more conditions in the prospective arm as compared to historical controls. Statistical testing for these endpoints will be performed using a logistic regression model with covariates as specified above for the primary analysis, and with propensity scoring adjustment as specified for the alternative analysis.

- Reduction in occurrence of one or more major neonatal morbidities with high likelihood of major chronic illness (MNM): cystic periventricular leukomalacia,

- grade 3 and 4 intraventricular hemorrhage, grade 3 or higher retinopathy of prematurity, bronchopulmonary dysplasia.
- Reduction in the rate of PTB <35 weeks, <32 weeks and <37 weeks of gestation. This analysis will be repeated for premature neonates delivered after spontaneous rupture of membranes or spontaneous onset of labor with gestational age at birth <32, <35 and <37 weeks vs. all other neonates.
- Reduction in NICU admission rates in the immediate neonatal period prior to initial discharge or neonatal death. This analysis will be repeated for all premature neonates, and for premature neonates delivered after spontaneous rupture of membranes or spontaneous onset of labor.

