6.1 Potential bias in the hybrid study

In this study, it is crucial to address selection bias, epoch bias, bias from self-selection of compliant completers in the higher-risk group, as well bias due to COVID-19 / SARS-CoV-2 exposure in the last ~400 subjects. Selection bias is the bias introduced by the selection of individuals, groups or data for analysis in such a way that proper randomization is not achieved, thereby ensuring that the sample obtained is not representative of the population intended to be analyzed. In this study, prospective intervention group and historical cohort study group are not allocated through randomization, therefore selection bias may be one of the important issues to be addressed. As the prospective arm and historical controls received care in different periods, epoch effects from trends in patient care and in public health may also prove an important source of bias. Finally, incomplete acceptance of interventions by some higher risk subjects in the prospective arm provides a source of bias that cannot be directly adjusted, as no higher risk group defined by PreTRM® risk score is present amongst the historical controls. Bias due to comparison of historical controls from a pre-pandemic period to prospective subjects reaching term during the SARS-CoV-2 pandemic has been ameliorated by restriction of the study to subjects reaching term before detection of the first SARS-CoV-2 positive case in Delaware.

Bias from any source will cause the distortion of a statistical analysis. Bias can have varying effects, and the magnitude of its impact and the direction of the effect are often hard to determine. If bias is not taken into account, the results and conclusions of the study may be false or misleading. Therefore, it is necessary to consider the sources of bias in the outcomes analysis.

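### The pandemic cut-off for the prospective arm is worded as reaching 37 0/7 weeks, which taken literally excludes preterm births from that arm only; the SAP's own counts and analyses imply a calendar rule that it never states

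*SAP*

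**What the plan says.** The prospective cohort for the primary analysis is described in three places, each time by gestation attained:

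- Section 4: "the primary analysis of the study will be limited to an estimated 1,453 subjects who reached" 37 0/7 weeks before local spread of the virus in Delaware and the associated research shut-down.
- Section 2 (Executive Summary): "An estimated 1,453 prospective subjects reached a gestational age of" 37 0/7 weeks before the same events.
- Section 6.1: bias is said to be reduced by "restriction of the study to subjects reaching term before detection of the first SARS-CoV-2 positive case in Delaware".

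The stated purpose in Section 4 is "To avoid bias in comparison of pre-pandemic controls to prospective subjects who reached term during the pandemic period".

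The controls are selected differently. Section 2 says that about 10,000 "women meeting the screening protocol will be identified with delivery prior to July 6th, 2018", and Section 5.1 takes all eligible attendees in the period. Neither sets a gestation condition.

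Section 5.1 defines the ITT, mITT and other populations without mentioning the pandemic cut-off. The only operative text for the restriction is therefore the wording above. No section gives a calendar date or a rule based on the due date.

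**The concern.** Reaching 37 weeks undelivered is the outcome the strategy is meant to bring about. A cohort rule that requires it in one arm only selects on that outcome. Both co-primary endpoints (NMI and neonatal hospital stay) and both secondary endpoints (NICU stay and duration of gestation) depend heavily on preterm birth, so anyone who coded the rule as written would build a difference in favour of the intervention into all four.

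The wording also allows a middle reading, in which a woman counts if she had reached 37 weeks or had already delivered by the cut-off. That gives yet another cohort. In addition, the cut-off event is not the same throughout: Sections 2 and 4 use local spread and the research shut-down, and Section 6.1 uses the first positive case. In a non-randomised comparison with historical controls, the cohort rule should leave nothing to choose.

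**Working it through.** **Inputs from the SAP.** Enrolled 1,873; primary prospective cohort 1,453; controls about 10,000; preterm birth rate 9.1%; NMI of 3 or more expected in 0.036 of controls and 0.020 to 0.023 of the prospective arm; screen-positive rate 34%; compliance 55% (all Section 4). One-tailed tests (Section 5). Holm across two co-primaries at 0.05 (Sections 4 and 5.5), so 0.025 at the first step.

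**Step 1. The plan's own power figure.** Section 4 states 0.7 to 0.9 for NMI by a one-sided Fisher test. Exact enumeration at 0.025 gives:
- 1,453 v 10,000: 0.753 (at 0.023) to 0.925 (at 0.020).
- If higher-risk women who do not start treatment leave the mITT, 1,453 x (1 - 0.34 x 0.45) = 1,231 v 10,000: 0.679 to 0.878.

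The stated range is reproduced at its one-decimal precision. It does not distinguish between readings of the cohort rule.

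**Step 2. Which reading do the counts fit?**
- Calendar reading: 1,873 - 1,453 = 420 women excluded. Section 6.1 speaks of pandemic "exposure in the last ~400 subjects". These agree.
- Literal reading: 1,453 women who reached 37 weeks would come from 1,453 / 0.909 = about 1,598 women, with 1,598 - 1,453 = about 145 preterm births also removed. Pandemic exclusions would then be 1,873 - 1,598 = about 275, which does not fit about 400.

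**Step 3. Which reading do the planned analyses fit?** Several need preterm births in the prospective arm:
- Section 5.6: the bottom quantile of gestational age at birth.
- Section 5.7: "Reduction in the rate of PTB <35 weeks, <32 weeks and <37 weeks of gestation"; stays of premature neonates; steroid timing before delivery under 37 weeks, compared within the prospective arm as well as with controls.
- Section 4: simulations that shift a gestational-age distribution with a 9.1% preterm rate.

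On the calendar reading about 0.091 x 1,453 = 132 preterm births would be expected with no treatment effect. On the literal reading there are none, and the rate under 37 weeks is 0% against about 9.1% by construction.

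**Step 4. Size of the error if the rule is followed literally.** Assume no treatment effect. Let f be the share of NMI 3-or-more cases that are preterm births. The SAP does not give f, so a range is shown. The rate among term births is 0.036 x (1 - f) / 0.909. The cohort is 1,453 women, all term, v 10,000 controls at 0.036; one-sided Fisher at 0.025:

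| f | Prospective rate | Chance of rejection |
|---|---|---|
| 20% | 3.17% | 0.11 |
| 30% | 2.77% | 0.35 |
| 50% | 1.98% | 0.93 |
| 60% | 1.58% | 0.996 |
| 70% or more | 1.19% or less | about 1.0 |

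On the calendar reading the rate is 0.036 in both arms and the test rejects in 0.021 of trials, below the nominal 0.025.

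At f = 50% the artefact alone gives 1.98%, close to the 2.0% to 2.3% that Section 4 expects from real benefit. The two could not be told apart by size.

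**Step 5. The middle reading (reached 37 weeks or already delivered).** The 420 later women are spread over about 17 weeks of gestation (20 to 37), or 420 / 17 = about 25 a week. A later woman is added if she delivered preterm before the cut-off and her 37-week date falls after it. The expected number is 25 x 0.091 x (mean weeks before 37 at preterm delivery). For an assumed mean of 1 to 4 weeks this is about 2 to 9 extra preterm births, which moves the rate from 9.1% to about 9.2% to 9.7%. The bias is small and runs against the intervention.

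**The case against.** The strongest reply is that no one meant to exclude preterm births. The purpose is to avoid a pandemic epoch effect, no section says that preterm births are removed, the mITT definition has no 37-week condition, and the counts and planned analyses in Steps 2 and 3 fit only a calendar cut-off. This stands. A reader might infer from the wording that the plan strips every preterm birth from the prospective arm and so produces a false positive. The documents do not support that conclusion; they show a rule whose literal sense conflicts with everything around it.

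Two further limits stand. The Fisher test is the one used for power in Section 4, whereas Section 5.5 specifies a weighted ordinal logistic regression with covariates. The rejection rates are therefore an approximation, not the error rate of the planned analysis. They also depend strongly on f: at 20% the inflation is to 0.11, not to near certainty. A reader might also subtract 132 preterm births from the 1,453. That mixes two readings, because on the literal one the 1,453 already contain none.

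What the reply does not do is supply a rule. The intended cohort has to be worked out by subtraction and from the endpoints, and even then the due-date reading and the middle reading remain open.

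**Conclusion.** The point holds as a defect in the stated rule. As written, the cohort restriction depends on the outcome in one arm only, and it contradicts the SAP's preterm analyses, its 9.1% preterm simulations and its count of about 400 late subjects. A calendar cut-off that keeps preterm births is the likely intent, and under it this rule causes no inflation.

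The consequence if the text is followed literally is serious: a false-positive chance for NMI of about 0.11 to nearly 1.0 as f goes from 20% to 60% or more, and a preterm rate of 0% by construction. This assumes no treatment effect, controls at 3.6%, a 9.1% preterm rate, and the Fisher test in place of the ordinal model. The inference from the counts in Step 2 assumes the 9.1% rate in the prospective arm and that women outside the 1,453 were left out for the pandemic or, on the literal reading, for preterm birth. The differing cut-off events are a lesser inconsistency whose effect cannot be sized from the document.

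**What to change.** In Sections 2, 4 and 6.1, and in the population definitions of Section 5.1, state one rule: the primary analysis includes every enrolled woman whose projected 37 0/7-week date (estimated due date minus 21 days) falls before a single fixed calendar date, whatever her actual gestational age at delivery. Give that date and remove the two differing event descriptions. Do not define the cohort by delivery before the date, since that would bring in early deliveries from later enrollees.

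Then recount the cohort under this rule and confirm or correct 1,453. The date and rule should be fixed without reference to outcomes. The cost is a change of wording and a recount; the due date is already defined in Section 3.7 and no new data are needed.

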5.1 Analysis Populations

One control population will be considered in primary analyses: the historical control population. The historical control population includes all subjects who attended ChristianaCare during the eligibility period and who satisfy all eligibility criteria.

The historical control arm will be the control population for primary and alternative analysis of the primary, secondary and exploratory endpoints.

Seven subject populations will be considered in the analyses: an Intent-to-Treat (ITT) population, a modified ITT population, a completer(s) population, a compliant completers population, a non-intervention completers population and a safety population. The completers, compliant completers, non-intervention completers and modified ITT populations are subsets of the ITT population.

The ITT population includes all historical subjects selected and all prospective patients enrolled regardless of whether or not the co-primary outcomes were observed, or in the prospective arm, any PreTRM test result has been generated or intervention consent has been signed. Subjects with missing outcomes will be handled as described in the missing data sensitivity analyses.

The modified ITT (mITT) population includes all subjects for whom both co-primary outcomes are known; and who have either been selected for the historical control group, received a not-higher-risk PreTRM® test result, or consented to and initiated treatment before 24^{0/7} weeks gestation after receiving a higher risk PreTRM® test result.

The completers population includes subjects for whom both of the co-primary outcomes are known, and, in the prospective arm, for whom a PreTRM® test result was generated.

The compliant completers population includes ITT subjects who have missed no more than 20% of daily doses for both low-dose aspirin and vaginal progesterone, and participated in weekly care management calls with no more than 20% missed weeks.

The non-intervention completers population includes all ITT subjects who received a higher-risk PreTRM® test result but neither consented to nor initiated treatment before 24^{0/7} weeks gestation.

The safety population includes all eligible subjects who gave consent to participate in the study and attempted a blood draw for the PreTRM® test, regardless of receipt of study interventions.

